## Organization and collaboration

PRISMA-PET is intended to be a part time PhD-project spanning 4 years. It is planned to be one of several projects in a larger research program established in a collaborative research center, entitled: Personalized

Assessment of Prostate Cancer: A Research Centre in Clinical and Translational Molecular Medicine (PASSPORT). PASSPORT represents a multidisciplinary collaborative team.

The overall purpose of PASSPORT is research, development and implementation of novel molecular imaging modalities and theranostic methods in PCa. The PRISMA-PET project focuses on the performance of  $^{18}\text{F}$ -PSMA PET/CT and PET/mpMRI in primary staging of intermediate and high risk PCa.

Other parallel PASSPORT projects in the clinical work package intend to investigate  $^{18}\text{F}$ -PSMA in recurrent and metastatic PCa, impact on clinical decision making and response monitoring, and treatment of progressive metastatic PCa with  $^{177}\text{Lu}$ -PSMA. Other work packages in PASSPORT aim at developing new therapeutic radiopharmaceuticals and at profiling PCa with biomarkers and genomic profiling. Several medical specialties and departments from OUH and intentionally from departments of other hospitals in RSD will be participating in PASSPORT center. Already participating specialties from OUH include nuclear medicine, urology, oncology, pathology, clinical biochemistry and clinical genetics, thus representing a truly multidisciplinary approach.

## Patient involvement

We have included two patient representatives in our study group to:

- Contribute in the development of information material for study participants.
- Contribute with valuable input in relevant project meetings when discussing patient related issues as well as ethical considerations.
- Aid in communicating study results to citizens, e.g. via the Danish prostate cancer patient organization "Prostatakræftforeningen" - PROPA.

## International collaboration

Collaboration, including study visits, with the "Munich-group" and/or the "Heidelberg-group" with regards to PSMA-expertise is considered relevant, but not yet formalized.

## Feasibility

Patient recruitment will be performed in collaboration with relevant departments of urology in RSD. One or more parallel PhD-projects on the same study population, but nested in the Department of Urology, OUH, is planned, thereby enabling patient recruitment on either of the two departments in close cooperation. It is considered achievable to include the required 448 patients in this setting.

The Department of Nuclear Medicine, OUH, received approval to produce  $^{18}\text{F}$ -PSMA-1007 from the Danish Medicines Agency in 2019.  $^{18}\text{F}$  will routinely be produced on our two cyclotrons, and our well-equipped radiochemistry is trained in the production and labelling of a wide variety of PET-tracers complying with Good Manufacturing Practice (GMP). The tracers will be shipped to the cooperating departments. We currently have five state-of-the-art PET/CT-scanners and a PET/MRI-scanner, and will as such have all the

prerequisites for tracer production and performing the planned scans together with the cooperating Nuclear Medicine Departments.

The PSMA-PET scans performed in OUH will be evaluated and documented as in clinical practice by the applicant and three supervisors as well as a PhD student from another PhD-project - all being Nuclear Medicine specialists along with specialists in radiology, and the same set-up is planned in the cooperating departments. Conventional scans will be evaluated as part of the daily routine at the Departments of Nuclear Medicine (NaF-PET) and Radiology (CE-CT, mpMRI). The SharePoint and RedCap systems will be used for data collection and management in line with the European data protection regulation (GDPR) implemented by May 25 2018. Sharepoint will be used for safe storage of permissions and registrations, and REDCap for patient data.

## Ethical aspects

All study procedures will be performed after having obtained informed consent from each patient. The project will be performed according to this protocol, comply with the Declaration of Helsinki and ICH-Good Clinical Practice guideline and relevant legislation (GDPR, the Health Act and the Data Protection Act) and as well as follow procedures for control of quality. If the protocol is not strictly followed, the sponsor will be informed by the principal investigators by mail or telephone. Approval is obtained by the local Ethical Committee (S-20190161 11-12-2019 and 31-03-2020) and the study protocol has been registered at the Danish Data Protection Agency (20/20086, 01-05-2020) . The study will be registered at the international clinical trial-registries (clinicaltrials.gov) before it is initiated. The patients are insured as a part of the clinical set up. No extra insurance is taken.

The critical data of the project will be the time point for progression, determined by the second of two following PSA blood tests with rising values. Time of death will be registered, possibly from our personal register. QoL questionnaires will be evaluated statistically.

Radiation dose for each element of the different scan types are estimated to:

- NaF-PET: 4.8 mSv from NaF and 3-6 mSv from low-dose CT, i.e. 7.8-10.8 mSv.
- F-PSMA PET/CT: 3.1-4.6 mSv from PSMA and 10 mSv from CE-CT, i.e. 13.1-14.6 mSv
- mpMRI gives no radiation dose

Radiation dose from staging by conventional imaging in group A will add up to 17.8-20.8 mSv. Patients in group B will receive a total of 20.9-25.4 mSv from F-PSMA PET/CT and the blinded NaF-PET, i.e. an additional radiation dose of up to 7.6 mSv. As annual background radiation dose in Denmark amounts to 3-5 mSv and the patient population consists of primarily middle-aged to elderly patients, the added radiation dose in group B is considered well within limits of reason.

## Planned publications

1. Clinical impact on stage migration and treatment strategy when using 18F-PSMA PET/CT compared to conventional imaging in primary staging of PCa (Group A vs B).

2. A prospective comparative accuracy study of 18F-PSMA PET/CT for N- and M-staging compared to conventional imaging in primary PCa (Group B).
3. The added value of PSMA-PET/mpMRI compared to PSMA-PET/CT on T, N, and R-staging (R = resection level) (Subgroup of B).
4. The impact on progression free survival and biochemical relapse when using 18F-PSMA PET/CT compared to conventional imaging in primary staging of PCa (Group A vs. B - planned as a joint publication with PhD student from the Department of Urology).

It is the intention to publish the results no matter if they are positive, negative or inconclusive. The results will be published in [www.clinicaltrialsregister.eu](http://www.clinicaltrialsregister.eu).

Authorship order will be depending on work effort and involvement according to the Vancouver Declaration (IMJCE). No clauses agreed.

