## Problem, aim, and hypothesis

Molecular targeting treatments and diagnostics in Prostate cancer (PCa) have evolved in recent years, while mortality from PCa has remained unchanged in Denmark (1). One molecular target is the prostate specific membrane antigen (PSMA), which is overexpressed in prostate cancer cells and can therefore serve as target for diagnosis, staging, and treatment. Positron Emission Tomography (PET) / Computed Tomography (CT) with radiolabelled PSMA (PSMA-PET/CT) has recently been implemented in the Danish Prostate Cancer guidelines (DAPROCA) as a potential tool for detecting relapsing local and metastatic disease. This decision is based on convincing studies showing a superior diagnostic accuracy of PSMA-PET/CT compared to conventional imaging in this patient setting (1).

When it comes to initial staging in primary PCa, however, there are only small diagnostic studies available performed retrospectively in heterogeneous study designs (2), and accordingly guidelines still recommend conventional imaging with contrast enhanced CT (CE-CT) and bone scintigraphy (BS) for staging in this setting(1). We believe that there is a need for larger prospective trials analyzing effects in terms of benefit for patients and society of implementing radiolabelled PSMA-PET/CT compared to conventional imaging for N-staging (lymph node metastases in the pelvic region) and M-staging (lymph node metastases outside the pelvic region, bone metastases and metastases in other organs).

The overall aim of this project is in a randomized design to compare  $^{18}\text{F}$ -PSMA-PET/CT to conventional imaging for initial staging in intermediate and high risk PCa with regard to accuracy, impact on treatment strategy and progression free survival. In a subgroup analysis we aim to analyze the added value of  $^{18}\text{F}$ -PSMA-PET/Magnetic Resonance (MR) for local staging.

We hypothesize that

- *Staging intermediate and high risk PCa with  $^{18}\text{F}$ -PSMA PET/CT and PET/MRI is more accurate at local-, N- and M-staging compared to conventional staging and therefore will lead to a change in treatment strategy with improved progression free survival.*

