## Background

PCa is the most frequent cancer form in men in developed countries (3) with approximately 4,500 new cases reported annually in Denmark, 980 of which are based in the Region of Southern Denmark (RSD). The relative 5-year survival is 87% (4). The course of disease ranges from well differentiated tumors localized to the prostate gland itself, being potentially curable, to aggressive, rapidly disseminating variants with poor prognosis despite intensive treatment.

Choice of treatment regimen at primary diagnosis is based on risk stratification, staging of the disease, and general health condition of the patient (1, 5). In intermediate and high risk PCa, further staging procedures besides T-staging (6) is warranted. CE-CT or magnetic resonance (MR) is used for N-staging in cases when pelvic lymph node dissection is avoided during radical prostatectomy or when surgery is refrained from (7), although either modality has a reported sensitivity of approximately 40% (8). M-staging is traditionally obtained from BS, which reflects bone metabolism and has a reported sensitivity as well as specificity of

80% (9). An alternative modality reflecting bone metabolism is the  $^{18}\text{F}$ -sodium fluoride PET/CT (NaF-PET) which has a superior accuracy compared to BS (10, 11). BS has been substituted with NaF-PET in clinical routine at our department, and will as well in this study. Multiparametric MRI (mpMRI) of the pelvis may be performed in high-risk patients for accurate T-staging and thereby planning of resection level (R-staging) before radical prostatectomy.

The treatment regimens for different stages of PCa ranges from observation, radiation therapy, radical prostatectomy and androgen deprivation to intensive chemotherapy and experimental therapeutic regimens (1, 5). The treatment regimens are associated with a specific risk of potential adverse effects, so correct staging is paramount in order to avoid unnecessary treatment complications. Curatively intended surgery or radiation treatment followed by a surveillance program is the initial intervention for patients with localized disease.

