## Research plan

The study is planned in a prospective randomized controlled design as illustrated in appendix 1 and 2 and will be carried out in close collaboration with the Department of Urology. The patients will be included and randomized as a part of one of the initial doctors appointments in a consultation room, and they will be encouraged to bring a relative to this consultation. Patients are identified when they have an appointment at Department of Urology, and the researchers will be given information from the clinicians, which means that they will not access the patient journals before enrolling. The patients will be informed about the project from the PhD-student, a physician from the Nuclear Medicine Departments, an Urologist from the cooperating departments or a nurse involved in the project, all with expertise in prostate cancer. They will be offered time to consider enrolment in the trial. The patients will be offered further information and answering of upcoming questions over the telephone after the initial talk. At this time or one of the following days, when they have accepted to be enrolled in the project and signed the written consent, they will be randomized in REDCap, where the randomisation code is kept. The randomization will be stratified according to the patients clinical risk status and pathology of biopsies. The written consents will be collected at the Nuclear Medicine Department, when they meet for their scan and at the earliest the day after the information in Department of Urology. Our study population will comprise men with a newly diagnosed intermediate or high risk (including locally advanced) PCa (1) or with a clinical suspicion of metastases based on other findings. Included patients will be randomized into a control group (A) and an interventional group (B). Group A will be staged by conventional imaging, i.e. CE-CT for N-staging and NaF-PET for M-staging. Group B will be staged by F-PSMA PET/CT for both N- and M-staging. A subset of patients with risk of extracapsular extension considered for radical prostatectomy in group B will also have an F-PSMA-PET/mpMRI-scan for T-staging (evaluation of the tumor). This scan will be performed in continuation of the F-PSMA-PET/CT, i.e. on the same administered dose of F-PSMA. Furthermore, a subgroup of patients in group B will have a blinded NaF-PET-scan for the purpose of performing comparative accuracy analyses.

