Biopsy of suspected metastatic lesions in N- and M-positive patients (suspicion of metastases) as well as lymph node specimen in N- and M-negative patients will be intended as reference standard in both groups as well as a nadir unmeasurably low post-surgery prostate specific antigen blood sample to indicate no residual disease where applicable. Reference standard in the accuracy analysis of F-PSMA PET/mpMRI with regard to T- staging is histopathology on surgical specimen. As the risk of distant metastases increases with increasing PSA-levels, analyses will be performed on both population level as a whole as well as in two PSA-strata with cut-off being PSA=100 ng/ml.

Treatment and subsequent follow-up will be planned on the basis of the results of the scans and according to current guidelines (1, 5).

Follow-up data will be collected from patient journals by the researcher/principal investigator or a delegate, and will consist of clinical information, examination reports, blood test results, information about treatments and pathology reports, all performed in a clinical setup as determined by the clinician. No extra visits, scans or blood test are required except for questionnaires. The patients will be asked to fill in questionnaires (EQ-5D-5L, FACT-P and EPIC 26) concerning quality of life during at baseline and 3, 6, 12, 24, 60, 120 og 236 months after recruitment. The questionnaires will be delivered to the patients e-boks from REDCap automatically at the specific time points. All collected information will be used in this project for analysis of treatment decision, relapse detection, overall survival and quality of life in the two patient groups.

Primary endpoints (Group A vs. B)

1. Treatment strategies and progression-free survival
2. Quality of life measures

Secondary endpoints

1. Overall survival (Group A vs. B)
2.  $^{18}\text{F}$ -PSMA-PET/MR for evaluation of extension of tumor in the prostate gland and surrounding structures compared to histopathology on surgical specimen.
3. Accuracy of  $^{18}\text{F}$ -PSMA-PET/CT compared to NaF-PET/CT for evaluation of bone metastases

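### PSMA-PET/mpMRI is never compared with mpMRI alone, so the hypothesis that it improves on conventional local staging is not tested

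*Combined protocol and SAP*

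**What the plan says.** - **Aim and hypothesis** (Problem, aim, and hypothesis). The aim reads "In a subgroup analysis we aim to analyze the added value of" PSMA-PET/MR for local staging. The hypothesis is that staging with PSMA PET/CT and PET/MRI "is more accurate at local-, N- and M-staging compared to conventional staging".
- **Existing scan for local staging** (Background). Multiparametric MRI "may be performed in high-risk patients for accurate T-staging and thereby planning of resection level (R-staging) before radical prostatectomy". The Feasibility section also lists mpMRI among the conventional scans, read routinely in Radiology.
- **Group A imaging** (Research plan). Conventional imaging is "CE-CT for N-staging and NaF-PET for M-staging". No imaging test is assigned to T-staging there.
- **Who gets PET/mpMRI** (Research plan). A subset of Group B: men who may have extracapsular spread and are candidates for prostatectomy. They are scanned on the same tracer dose as the PET/CT. The size of the subset is not given.
- **Secondary endpoint 2** (Research plan). PET/MR is assessed "for evaluation of extension of tumor in the prostate gland and surrounding structures compared to histopathology on surgical specimen". No comparator test is named.
- **Study 3** (Planned publications). "The added value of PSMA-PET/mpMRI compared to PSMA-PET/CT on T, N, and R-staging (R = resection level) (Subgroup of B".
- **Sample size and statistical analyses.** The only accuracy sample size, 128, rests on the prevalence of metastases. The PET/mpMRI subset is not mentioned.

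**The concern.** A claim that a new test is more accurate than conventional staging needs the conventional test as comparator. For T-stage and resection level before surgery, the only imaging test that the protocol names is mpMRI, and mpMRI is also one component of the new test. Neither planned evaluation separates the two components:

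- Histology is a reference standard. Measured against it, PET/mpMRI yields an accuracy figure for the combined scan, with nothing to set it beside.
- PSMA-PET/CT shares the PSMA-PET component. The contrast shows what mpMRI in place of CT does when PSMA-PET is present in both.

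At stake is whether the trial can say anything about its own local-staging hypothesis. The change in treatment intent planned as an outcome of study 3 has the same limit: a change relative to PET/CT does not show what PSMA-PET contributes beyond mpMRI.

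**Working it through.** **1. Which comparisons are planned**

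| Comparison for local staging | Planned? | Where |
|---|---|---|
| PET/mpMRI against surgical histology | Yes | Research plan, secondary endpoint 2 and reference standard |
| PET/mpMRI against PSMA-PET/CT | Yes | Planned publications, study 3 |
| PET/mpMRI against mpMRI alone, same men | No | Not in any section |
| PET/mpMRI against T-staging in Group A | No | Group A imaging is assigned to N- and M-staging |

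The protocol gives no accuracy assumption, power or size for the subset, so there is no stated figure to reproduce.

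**2. What the planned contrast estimates**

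Let s(CT), s(M) and s(PM) be the sensitivities for extracapsular extension of PSMA-PET/CT, mpMRI alone and PSMA-PET/mpMRI. Then

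s(PM) − s(CT) = [s(PM) − s(M)] + [s(M) − s(CT)].

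The first bracket is what PSMA-PET adds to mpMRI. The second is the difference between mpMRI alone and PET/CT. Study 3 estimates only the sum. Without a separate reading of mpMRI, s(M) is not observed and the sum cannot be split. The same holds for specificity.

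**3. Illustration (all sensitivities assumed)**

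Take s(CT) = 0.30 and s(PM) = 0.62. The planned contrast is 0.62 − 0.30 = 0.32.

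- If s(M) = 0.60, PSMA-PET adds 0.62 − 0.60 = 0.02.
- If s(M) = 0.40, PSMA-PET adds 0.62 − 0.40 = 0.22.

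The planned result is the same in both cases.

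**4. The planned contrast when PSMA-PET adds nothing to mpMRI**

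Set s(PM) = s(M). The planned gain is then s(M) − s(CT). The table gives the probability that an exact two-sided McNemar test at 5% favours PET/mpMRI, by the number of histology-positive men. It takes the errors of the two tests as independent, so the discordant probabilities are s(M)[1 − s(CT)] and s(CT)[1 − s(M)]. For 0.60 and 0.30 these are 0.60 × 0.70 = 0.42 and 0.30 × 0.40 = 0.12, a difference of 0.30.

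| s(CT) | s(M) | Planned gain | 20 men | 40 men | 60 men |
|---|---|---|---|---|---|
| 0.30 | 0.60 | 0.30 | 34% | 70% | 88% |
| 0.30 | 0.70 | 0.40 | 59% | 93% | 99% |
| 0.40 | 0.60 | 0.20 | 15% | 34% | 51% |
| 0.40 | 0.70 | 0.30 | 34% | 70% | 88% |
| 0.50 | 0.60 | 0.10 | 5% | 10% | 14% |
| 0.50 | 0.70 | 0.20 | 15% | 35% | 52% |

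Across these assumptions the planned gain is 10 to 40 points. The chance of a significant result is 5 to 59% with 20 positive men, 10 to 93% with 40, and 14 to 99% with 60. PSMA-PET's increment over mpMRI is zero in every row. Independence is a simplification, since both scans use the same tracer dose in the same man. The algebra in step 2 needs neither independence nor these values.

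**The case against.** **Study 3 asks a legitimate question.** Group B is already staged by PSMA-PET/CT, and the PET/mpMRI follows on the same dose. Whether the further scan adds to the one just done is a natural question, and the title of study 3 states it openly. This stands, and it is why that contrast should remain as planned. It does not answer the separate hypothesis about conventional local staging.

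**A reader might infer that a gain due to mpMRI would be credited to PSMA.** The documents do not support that. PSMA-PET is on both sides of the contrast, so a gain would be credited to the combined scan relative to PET/CT, and the protocol nowhere says that study 3 isolates PSMA. The defect is a missing comparison.

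**A reader might also infer that study 3 will probably find PET/mpMRI better.** That rests on assumed sensitivities and an unstated subset size. The table above runs from 5% to 99%.

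**mpMRI is optional.** The Background says only that it may be done, in high-risk men, and Appendix 1 takes eligibility T-stage from rectal examination or ultrasound. It is therefore too strong to call mpMRI the required standard. However, no comparison of PET/mpMRI with rectal examination or ultrasound is planned either, so the local-staging hypothesis is untested on that reading too.

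**Group A may contain mpMRI.** This cannot be excluded: clinical mpMRI is allowed, examination reports are collected at follow-up, and the Appendix 2 flow chart could not be read. But no described analysis uses such scans, and clinically selected mpMRI in the other arm would not replace a paired reading in the same men.

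**The added comparison may be imprecise.** This stands. A small increment such as 0.02 could not be shown in a small surgical subset, so the comparison should be reported as an estimate and not as a powered test.

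**Conclusion.** The point holds for the hypothesis on local staging. That hypothesis sets PSMA PET/MRI against conventional staging, the protocol names mpMRI as the conventional scan for T-stage and resection level, and no section that could be read plans a comparison with it. Study 3 remains valid for what PET/mpMRI adds to PET/CT.

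The size cannot be derived from the documents. What PSMA-PET adds to mpMRI is not identified under the plan, whatever the sensitivities. The 10 to 40 point figure is an illustration only.

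The consequence is limited. It touches a secondary endpoint and one planned publication, in a subset of Group B. The randomised primary comparison and the sample sizes of 448 and 128 are unaffected. It is nevertheless worth correcting before the subset is read, because a reader who has already seen the PET cannot give an independent mpMRI report.

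**What to change.** 1. **Reading order.** In the PET/mpMRI subset, the existing readers report the mpMRI part of the scan first, without PET data from either the PET/MRI or the preceding PET/CT. They lock T-stage, including extracapsular extension, in REDCap. They then open the PET and record the combined read.
2. **Analysis.** Add to secondary endpoint 2 a paired comparison of PET/mpMRI with mpMRI alone, both against surgical histology. Report the differences in sensitivity and specificity with 95% CIs, and state the number of operated men.
3. **Keep the present contrast.** PET/mpMRI against PSMA-PET/CT stays as the planned contrast of study 3, described as what PET/mpMRI adds to PET/CT.
4. **If the separate read is not adopted,** narrow the hypothesis so that it does not claim a comparison with conventional local staging.

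The cost is a reading rule, REDCap fields for the locked mpMRI read and one paired analysis. No extra scan, radiation or reader is needed: the mpMRI is already acquired, and the Feasibility section already has radiology specialists reading alongside nuclear medicine. The drawbacks are slightly longer reading time and probably limited precision in a small surgical subset.
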